### 3.3.1.1 Justification for Comparator Selection (Alternative Treatment Strategy)

The alternative treatment strategy will be a SOC, non-user group, because in clinical practice, there is no alternative drug that would be prescribed instead of OM-85 for the prevention of RTIs. Other bacterial lysates would be an exception; however, those should not be used as the comparator (see below). When there is no clear alternative to the treatment of interest, patients who did not initiate the drug of interest (non-users) can be used as the comparator ([36](#)).

Patients treated with other bacterial lysates could have been a suitable comparator group considering the similarity of the indication, on prevention of RTIs, and thereby likely similar

baseline characteristics than OM-85 treated patients (limited confounding by indication). However, because the objective of this study is not to assess within-class effects they were discarded. In addition, the feasibility assessment demonstrated that the low number of patients treated with other bacterial lysates in the countries of interest would not enable a formal, analytical comparison (< 200 patients in Belgium, < 9,000 in Italy and 52 patients in China after applying the preliminary inclusion and exclusion criteria).

The chosen alternative treatment strategy (SOC/non-user group) is heterogeneous and will include a variety of RTI patients in differing disease stages, RTI frequency and severity. To enhance the comparability of the exposure groups at baseline, the SOC/non-user group will be restricted to patients with similar prognostic factors and probability of receiving OM-85 at CED, by matching on the PS.

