**Table 2 Events Ending Follow-up and Censoring Variables**

		Operational Definition
Events ending follow-up, throughout the follow-up		
1	End of 24-month follow-up	2 years from end of initiation grace period for each patient
2	Death	For THIN Italy and Belgium: last contact date, which defines exit from the database regardless of reason (death, physician change, or choosing to exit the database) For Inspur China: Date of death directly available by a report from social security sent to Inspur
3	Loss to follow-up/exit of data source	For THIN Italy and Belgium: last contact date, which defines exit from the database regardless of reason (death, physician change, or choosing to exit the database) For Inspur China: Date of lost to follow-up, which defines exit from the database regardless of reason (death or migration to another city)
Censoring during follow-up, after the 30-day initiation grace period: deviation from the assigned treatment strategy		
1.1	OM-85 group: None	-
1.2	SOC/non-user group: at first date of OM-85 prescription during follow-up (after the initiation grace period)	Same
1.3	Sensitivity analysis: The SOC/non-user group are censored at the first date of prescription for any bacterial lysate (including OM-85), the OM-85 group would be censored at the first date of prescription of any bacterial lysate other than OM-85 during follow-up	Same

Note: CED: cohort entry date; SOC: standard of care; THIN: The Health Improvement Network.

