**Table 6 Treatment Strategies (Exposure Groups)**

OM-85 group	Patients initiating preventive treatment with OM-85	Initiation of OM-85 at CED or 30 days after (during the 30-day initiation grace period), defined at the first observed prescription of OM-85 during this time, using country-specific drug codes ( Appendix 4 ) The patients are “new users”, as no prescriptions of any bacterial lysates are allowed in the 12-month baseline period. Preventive treatment is considered static; no censoring is applied in follow-up at deviation from treatment strategy. In a sensitivity analysis, patients will be censored at date of the first prescription of another bacterial lysate ( Section 3.7.7 ).
SOC/non-user group	Patients not initiating OM-85	SOC/non-user group: No initiation of OM-85 at CED or 30 days after (during the 30-day initiation grace period). Censoring at first record of OM-85. In a sensitivity analysis, patients will also be censored at date of the first prescription of another bacterial lysate than OM-85 ( Section 3.7.7 ).

Note: CED: cohort entry date; SOC: standard of care.

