### 3.5 Study Size

In this non-interventional study, all patients available in the databases will be included in the study population. Based on the feasibility assessment, 14,362 patients meeting inclusion criteria and using OM-85 are available in Belgium (of which 10,555 patients aged  $\geq 18$  years old), 3,219 patients in Italy (of which 2,742 patients aged  $\geq 18$  years old), and 8,656 patients in China (of which 1,338 patients aged  $\geq 18$  years old). The study size is based on including the maximum number of patients for the OM-85 group. However, the strategy to include patients to this study using the TTE framework is not identical to the feasibility assessment, and fewer OM-85 exposed patients will be included in this full study using the TTE framework ([Section 3.9.5](#)).

For primary objective 1, the study size required to estimate the difference between rates of two groups (pre- and post- OM-85 treatment) is evaluated based on the precision of the point estimate, as described below.

The CI for point estimate of incidence rate ratio (IRR) is calculated as follows ([38](#)), where a and b are the counts of events in each group, PT1 and PT2 are the person-time (in person-years [PYs]) in each group, and F is a quantile of the F distribution.

$$\widehat{\text{IRR}} \text{ CI} = \left( \frac{PT_2}{PT_1} \right) \left( \frac{a}{b+1} \right) \frac{1}{F_{\alpha/2, 2(b+1), 2a}} \text{ to } \left( \frac{PT_2}{PT_1} \right) \left( \frac{a+1}{b} \right) F_{\alpha/2, 2(a+1), 2b}$$

With a hypothetical population rate of 2 episodes per person per year in the baseline (based on reported Upper RTI global age-standardised incidence rate of 225,505 per 100,000 person-years, in the Global Burden of Diseases, Injuries, and Risk Factors Study [GBD] 2019 ([39](#))), and assuming equal person-time in the two groups, the width of the 95% CI for the estimated IRR under difference effect sizes and sample sizes are demonstrated in [Table 9](#).

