## 8.7 Appendix 7: Target Trial Specification and Emulation

**Table 13 Target Trial Specification and Emulation**

Protocol component	Target trial specification (hypothetical)	Target trial emulation for a non-interventional (observational) cohort study using healthcare databases	Justifications

Eligibility criteria
	
Inclusion criteria
 
 
• Aged <math>\geq 1</math> year at enrolment
 
• <math>\geq 1</math> RTI episodes within 12 months prior to enrolment
 
• No use of any bacterial lysates 12 months prior to enrolment
 
 
Exclusion criteria None.
	
Same, using the operational definitions for a secondary data.
 
Inclusion criteria
 
 
• Aged <math>\geq 1</math> years during the inclusion period
 
• <math>\geq 1</math> RTI episodes within a 12-month period during the inclusion period. The CED is the date of the 2nd, 3rd, ... or nth RTI episode (i.e., date of fulfilling this inclusion criterion)*
 
• <math>\geq 12</math> months of continuous enrolment in the database prior to the CED
 
• No record of prescription of any bacterial lysates within 12-months prior to the CED
 
 
Exclusion criteria None
 
* During the inclusion period, patients can have several CED. For these patients, the CED will be selected randomly, which is one of the unbiased methods to select the date. Patients are allowed to enter the study only once.
	
Inclusion criteria
 
 
• OM-85 is approved from 6 months of age. However, at minimum 12 months of baseline data are needed. Therefore, the minimum age at inclusion is 1 year.
 
• The included patients have to meet the indication for OM-85, to have as comparable exposure groups as possible. Hence, recurrent RTIs have to be an inclusion criterion.
 
• In the non-interventional study, a minimum of 12 months of baseline data are needed for each patient, for defining the inclusion criterion of no use of any bacterial lysates, baseline characteristics, and the rate of RTI episodes before inclusion to the study. This criterion would not be applied in a trial.
 
• Prescriptions of any bacterial lysates is not allowed, in order to include only new users of OM-85 and isolate the effectiveness of OM-85 from other bacterial lysates. Apart from OM-85, other bacterial lysates may have (partially) corresponding effect, and hence included patients will also have to be naïve to them. The term “prescription” is used because the available databases include prescription data.
 
 
Exclusion criteria
 
 
• No exclusion criteria are defined, because none of the considerations and precautions for OM-85 use described in the product information, such as pregnancy or hepatic and renal impairment, are strict contraindications for OM-85.
 

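### Patients who start another bacterial lysate at cohort entry or in the 30-day grace period count as SOC/non-users, and the planned sensitivity analysis does not reliably remove them

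*Protocol*

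**What the plan says.** **Who is a non-user.** Inclusion criterion 4 (Protocol Table 4) bars bacterial lysates in the 12 months before CED and no later. Table 6 then defines the SOC/non-user group as "No initiation of OM-85 at CED or 30 days after (during the 30-day initiation grace period". In the main analysis this group is censored at OM-85 only (Section 3.3.1; Table 2, row 1.2).

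**What the protocol thinks of other lysates.** Table 13 (Appendix 7) justifies the lysate-free baseline by noting that "other bacterial lysates may have (partially) corresponding effect". Section 3.3.1.1 rejects these drugs as comparator for two reasons. First, within-class effects are not an objective. Second, "the low number of patients treated with other bacterial lysates in the countries of interest would not enable a formal, analytical comparison", with feasibility counts of "< 200 patients in Belgium, < 9,000 in Italy and 52 patients in China". Section 3.5 gives the OM-85 counts: "14,362 patients meeting inclusion criteria and using OM-85 are available in Belgium" and "3,219 patients in Italy".

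**The safeguard.** A sensitivity analysis censors at other lysates. In Table 2 (row 1.3) it stands under the heading "Censoring during follow-up, after the 30-day initiation grace period: deviation from the assigned treatment strategy", and Section 3.2.1 starts comparative follow-up at the end of that period. Table 6 and Section 3.7.7 censor at the first prescription of another lysate and give no time window. The clone-censor-weight analysis in Section 3.7.7 starts at CED but, as described, censors clones on OM-85 alone.

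**The concern.** The baseline criterion is meant to separate OM-85 from the rest of its class, yet that protection ends at CED. From CED to day 30, the window in which exposure is assigned, a patient can receive another lysate for the same indication and enter the comparator as a non-user. If those drugs work, the SOC rate falls and the IRR for primary objective 2 moves towards 1. A reader would look to the other-lysate sensitivity analysis to show whether this matters, but it may leave these very patients in place. The OM-85 arm has the same gap: another lysate added in the grace period is not dealt with there either.

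Separately, the count offered as too low for a comparison is, in Italy, bounded by a figure well above the number of OM-85 users on which the study itself proceeds.

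**Working it through.** **Step 1. Trace one patient through the rules.** CED is day 0. Another lysate is prescribed on day 10, and OM-85 is never prescribed.

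| Rule | Result |
|---|---|
| Table 4, criterion 4 | Eligible: nothing in the 12 months before CED |
| Table 6 | SOC/non-user |
| Main analysis (Table 2, row 1.2) | Never censored for the lysate; up to 24 months counted as SOC |
| Sensitivity analysis, Table 2 row 1.3 | Censored only if a further lysate prescription falls after day 30; otherwise never |
| Sensitivity analysis, Table 6 and Section 3.7.7 | Censoring date (day 10) precedes start of follow-up (day 30); no rule says what then happens |
| Clone-censor-weight analysis | The SOC clone is not censored for the lysate |

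A patient with OM-85 on day 0 and another lysate on day 10 meets the same gap in the OM-85 arm.

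**Step 2. Size of the dilution in the SOC group.** Let t be the true IRR and s the share of SOC person-time on another lysate. Assume that the other lysate has the same rate ratio as OM-85 throughout follow-up. Then

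observed IRR = t / (1 − s + s·t).

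Example: t = 0.70, s = 0.10 gives 0.70 / (0.90 + 0.07) = 0.70 / 0.97 = 0.722. Share of the effect lost = (0.722 − 0.70) / 0.30 = 7.2%.

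| s | t = 0.70 seen as | effect lost | t = 0.90 seen as | effect lost |
|---|---|---|---|---|
| 5% | 0.711 | 3.6% | 0.905 | 4.5% |
| 10% | 0.722 | 7.2% | 0.909 | 9.1% |
| 30% | 0.769 | 23.1% | 0.928 | 27.8% |

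The protocol does not give s, so these are assumed values. A partial effect of the other lysates would shrink every entry. The formula covers the SOC group only.

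**Step 3. Where it can matter.** Ratio of other-lysate to OM-85 feasibility counts, using the bounds:

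- Belgium: 200 / 14,362 = 1.4% at most
- China: 52 / 8,656 = 0.6%
- Italy: 9,000 / 3,219 = 2.8 at most

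**Step 4. Is the Italian number low?** The only size benchmark in the protocol is Table 9: a 95% CI width of at most 0.2, reached at 350 person-years per group for IRR 0.9. With the F-based interval printed in Section 3.5, b = 2·PT2 and a = IRR·2·PT1, all 32 cells of Table 9 reproduce to within 0.0005. The width at IRR 0.9 and 350 person-years is 0.197, as stated. Applying the same formula at IRR 0.9 with an assumed 1 person-year per patient:

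| OM-85 vs other lysates | CI width |
|---|---|
| Italy 3,219 vs 9,000 | 0.053 |
| Italy 3,219 vs 1,000 | 0.092 |
| Italy 3,219 vs 500 | 0.122 |
| Italy, 10% of both retained (322 vs 900) | 0.171 |
| Italy, 5% of both retained (161 vs 450) | 0.243 |
| Belgium 14,362 vs 200; matched 200 vs 200 | 0.181; 0.262 |
| China 8,656 vs 52; matched 52 vs 52 | 0.360; 0.528 |

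The low-number argument is sound for China, and for Belgium if matched 1:1. For Italy it fails unless the count is far below its bound or selection removes nearly all patients. The benchmark assumes Poisson counts and was set for primary objective 1; overdispersion would widen the intervals.

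**The case against.** Several points on the other side stand.

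- **The contrast is consistently stated.** Section 2.1, Section 3.3.1 and Table 13 all compare starting OM-85 with not starting it. If Italian physicians use other lysates, that is arguably standard care. A reader might infer that the primary comparison fails to answer its own question. The documents do not support that: what is loose is the non-user label and its fit with Section 3.3.1.1.
- **The comparator choice survives.** A reader might infer from the Italian count that a lysate comparator was wrongly rejected, or that an Italian head-to-head analysis is owed. The within-class reason comes first and is untouched. The figure of 9,000 is also an upper bound under preliminary criteria, so the true ratio is unknown.
- **The issue is partly recognised.** Section 3.9.4 acknowledges other lysates in the follow-up of OM-85 initiators and applies the censoring analysis to both groups. Table 6 and Section 3.7.7 could be read as removing a grace-period starter at time zero. It is therefore too strong to say that such a patient certainly stays in; the text leaves it open, and Table 2 read literally keeps the patient.
- **Heavy contamination is not shown.** Suppose other lysates are started 2.8 times as often as OM-85 at every propensity p. Then s = 2.8p/(1 − p): p = 1% gives 2.8% (0.70 seen as 0.706) and p = 5% gives about 15% (0.732). Reaching 30% needs p near 10%, with the bound used as if it were the count. Nor do the documents show that matching favours these patients. Section 3.3.1.1 only calls their baseline characteristics likely similar.
- **Direction.** Dilution of the SOC group works towards the null, so it cannot create a false benefit.
- **Removing patients from SOC alone could leave a lower-risk comparator.** This is a fair warning, and a reason to apply any exclusion to both arms and before matching.

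**Conclusion.** The point holds as a gap in definition with a weak safeguard. Other-lysate starters at CED or in the grace period are SOC/non-users in the main analysis, and no planned analysis clearly removes them from either arm. Under an equal and lasting effect, 5% to 10% contamination would cost roughly 4% to 9% of the effect, and 30% would cost 23% to 28%. The true share cannot be derived from the protocol. Feasibility counts make the problem negligible in Belgium and China, so Italy is the country to watch. The low-number sentence is unsupported for Italy, but correcting it does not alter the choice of comparator.

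**What to change.** 1. In the other-lysate sensitivity analysis, exclude before propensity-score matching, in both arms, every patient with another bacterial lysate prescribed at CED or in the 30-day grace period. Then censor at the first other lysate during follow-up. Comparative follow-up starts at the end of the grace period, so the exclusion uses only information available by time zero.
2. Preferably use the same rule in the SOC definition of the main comparison, so that non-user means no bacterial lysate of any kind.
3. Make Table 2, Table 6 and Section 3.7.7 state one rule for grace-period starters, and say how other lysates are treated in the clone-censor analysis, where follow-up starts at CED.
4. Report the number of other-lysate starters by arm and country, so that the possible dilution can be judged.
5. In Section 3.3.1.1, limit the low-number argument to Belgium and China and let the within-class reason carry Italy. No Italian head-to-head analysis is required.

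Cost: a slightly smaller matched pool, mainly in Italy, and a few lines of text. The drug codes are already needed for inclusion criterion 4.

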### 3.3.1.2 Pattern of Prescribing OM-85 (Secondary Objective 2)

For the OM-85 group, the following will be defined to analyse treatment patterns:

- **OM-85 initiation date:** The OM-85 initiation date will be the date of the first observed prescription of OM-85 at CED or during the 30-day initiation grace period.
- **OM-85 renewal date:** The prescription date for each subsequent OM-85 prescription during the follow-up is an OM-85 renewal date.
- **Prescribed quantity:** Prescribed quantity is defined as the number of units (capsules or sachets) prescribed to the patient at OM-85 initiation and renewal dates.
- **Daily dose:** The dose is assumed to be 1 unit, i.e. capsule or sachet, per day (24), unless if a specific other daily dose is directly available in the database.
- **Prescribed dose:** The strength of the prescribed units, 7 mg or 3.5 mg, is considered the prescribed dose, unless if a specific other prescribed dose is directly available in the database.
- **Prescription duration:** The duration of each prescription is equal to the prescribed quantity (assuming the one unit per day), multiplied by 3 because OM-85 is prescribed in 10-day courses per month). For example, if a patient is prescribed 10 capsules, the duration of the prescription is 30 days. The start of the prescription duration is the OM-85 initiation or the renewed OM-85 prescription's start date (see definition below).
  - **Cumulative prescription duration of overlapping prescriptions:** If the OM-85 renewal date occurs before the previous prescription duration has ended (or at the end date), the durations of both (or more) prescription durations will be summed. For example, if the prescription duration of the first OM-85 prescription at OM-85 initiation date is 30 days (based on 10 prescribed units) and the patient receives another 30-day prescription 20 days after the OM-85 initiation date, the cumulative prescription duration is 60 days from OM-85 initiation date.

- **Renewed OM-85 prescription's start date:** The start date of a renewed prescription, which is defined as the OM-85 renewal date or the end of the (cumulative) prescription duration +1 day, whichever occurs later. For example (the same example as above), if the prescription duration of the first OM-85 prescription at OM-85 initiation date is 30 days (based on 10 prescribed units) and the patient receives another 30-day prescription 20 days after the OM-85 initiation date, the renewed OM-85 prescription's start date is 30 days +1 day, i.e. 31 days after the OM-85 initiation date.
- **Maximum allowable gap between OM-85 prescriptions, to define OM-85 cycles:** An OM-85 cycle is defined to end when no subsequent OM-85 prescription is observed after a maximum allowable gap (in days) since the most recent OM-85 prescription duration has ended. This maximum allowable gap is defined as 30 days after the most recent OM-85 prescription duration has ended. The OM-85 cycle ends at the end of this gap, i.e., 30 days after the most recent OM-85 prescription duration date, if no renewal is observed during this gap. For example, if the most recent prescription duration is 30 days from the renewed OM-85 prescription's start date, the OM-85 cycle ends 60 days after the renewed OM-85 prescription's start date (30-day prescription duration plus 30-day maximum gap), if no new renewal is observed before the end of this 60-day period.
- **OM-85 cycle duration:** The OM-85 cycle duration is defined as the time between the OM-85 initiation date and the end date of the maximum allowable gap, 90 days in the above example, consisting of the first prescription of 30 days, the subsequent prescription of 30 days, and the 30-day maximum gap.
- **2nd OM-85 treatment cycle:** If the patient receives a new prescription after the duration of the 1st OM-85 cycle has ended (i.e. after the maximum allowable gap), the date of that prescription is the start date of the 2nd OM-85 treatment cycle. The same above definitions will be applied to this 2nd cycle, as the 1st cycle, with the exception that the start date for the cycle is the start date of the 2nd OM-85 treatment cycle, not the OM-85 initiation date.
- **Interval between two OM-85 cycles:** The time between the end of the allowable gap of the 1st OM-85 cycle and the start date of the 2nd OM-85 treatment cycle defines the interval between the OM-85 cycles.

The treatment patterns of interest are detailed in [Section 3.3.2.2, Table 8](#).

